10.3. Procedures for Recording Adverse Events

All AEs occurring during the study that are observed by the Investigator or reported by the participant, will be recorded on the CRF, whether or not attributed to study medication.

The following information will be recorded: description, date of onset and end date, severity, assessment of relatedness to study medication, other suspect drug or device and action taken. Follow-up information should be provided as necessary.

The severity of events will be assessed on the following scale: 1 = mild, 2 = moderate, 3 = severe.

AEs considered related to the study medication as judged by a medically qualified investigator or the Sponsor will be followed either until resolution, or the event is considered stable.

It will be left to the Investigator’s clinical judgment to decide whether or not an AE is of sufficient severity to require the participant’s removal from treatment. A participant may also voluntarily withdraw from treatment due to what he or she perceives as an intolerable AE. If either of these occurs, the participant will undergo an end of study assessment and be given appropriate care under medical supervision until symptoms cease, or the condition becomes stable.

10.4. Reporting Procedures for Serious Adverse Events

SAEs will be recorded and deemed reportable for up to 30 days following last administration of a trial drug, whether occurring after the end of the trial or between trial phases following a prolonged washout period.

All SAEs (other than those defined in the protocol as not requiring reporting) must be reported on the SAE reporting form to the DSMB within 24 hours of the Site Study Team becoming aware of the event. It will also be reviewed at the next DSMB meeting. Additional and further requested information (follow-up or corrections to the original case) will be detailed on a new SAE Report Form and emailed to the DSMB as requested. The DSMB will review all AEs and SAEs on a yearly basis.

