8. STUDY PROCEDURES

Participants will be recruited from multiple sites within travel distance of the John Radcliffe Hospital in Oxford, but the study visits will take place in Oxford (see below).

Each participant will undergo a screening visit, a baseline visit (which can be combined with the screening visit if the test results required for determining eligibility are available) and 3 'on-medication' visits. The screening visit will incorporate an assessment of eligibility and detailed trial explanation, followed by informed consent. They will then have a full medical history and examination, review of medical records, ECG (if one is not available from the previous year) and blood tests (if none available in the previous 3 months). They will then have a baseline study visit, either combined with the screening visit, if the availability of screening results permit, or within 1 month. At the baseline visit, they will undergo a repeat medical history for any events since the screening visit, repeat screening blood tests or ECG (if indicated), a formal cognitive assessment and a physiological assessment. If all eligibility criteria are fulfilled, they will be then assigned a study ID and associated randomisation schedule, followed by provision of allocated medication by the clinical trials pharmacy. Participants will then take each of placebo, sildenafil or cilostazol for 3 weeks each, in random order, at low dose for 1 week followed by titration to full dose for 2 weeks (minimum 11 days). Patients on omeprazole will not increase the dose after one week (due to an interaction with cilostazol). After visits 1 and 2, there will be a minimum of a 1 week washout period prior to starting the new medication. On-treatment visits will include review for SAEs and a repeat core physiological assessment. All participants, up to a maximum of 60, will additionally be invited to undergo an MRI scan at follow ups on placebo and sildenafil (with up to thirty also being scanned on cilostazol).

For participants who are unable to attend an on-treatment study visit once their medication has been started (for example due to the COVID-19 pandemic), then they will be able to restart treatment at the

point of stopping treatment, if still during the titration phase, but otherwise will restart three weeks of treatment from the beginning. The washout period can be prolonged as long as is necessary during the COVID-19 outbreak, before the next treatment phase is started.

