8.6. Subsequent Visits

Participants will be reviewed at visits 2, 3 and 4 (3, 6-7 and 11-13 weeks respectively) following sequential, blinded treatment in random order with the study drugs, sildenafil and cilostazol, and placebo for 3 weeks. At each follow up visit they will undergo assessment of potential side effects or unwanted effects (SAEs/SUSARS – see below), including repeat clinical examination and repeat blood tests, as at the baseline visit. Concomitant medications will be recorded, and compliance with study drugs will be assessed by questionnaire and by counting of returned study drug.

Following clinical assessment, the physiological assessment will be repeated as the primary study outcome (pulsatility index). Then the next drug will be dispensed, and any residual drug will be returned.

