8.10. Definition of End of Study

The end of active patient management is the date of the last visit of the last participant (LVLP), but blood will be stored for up to 2 years after LVLP for analysis,

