NB: to avoid confusion or misunderstanding of the difference between the terms “serious” and “severe”, the following note of clarification is provided: “Severe” is often used to describe intensity of a specific event, which may be of relatively minor medical significance. “Seriousness” is the regulatory definition supplied above.

Any pregnancy occurring during the clinical study and the outcome of the pregnancy should be recorded and followed up for congenital abnormality or birth defect, at which point it would fall within the definition of “serious”.

Safety data will be routinely collected at each follow-up, including clinical history of side effects or adverse events, clinical examination and blood tests (FBC, U+Es, LFTs). Patients will also be provided a telephone number to contact in case of side effects, and if the side effects suggest possible hypotension, may be asked to perform additional BP monitoring.

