2.4 Statistical interim analyses, data review and stopping guidelines

The DSMB will review recruitment and safety data after 30 patients have been recruited to the study or 12 months after the first visit of the first patient (whichever is sooner) or at the request of the sponsor or CI. Data will be reviewed in a blinded form, except where significant SAEs (in the opinion of the DSMB) or a potentially important number of severe AEs have occurred, when the data will be unblinded upon the request of the DSMB. No efficacy or futility interim analysis is planned.

If after 12 months recruitment falls below the rate expected to complete the study in 3 years, allowing for delays due to the COVID-19 outbreak, the overall study size can be reduced to 50 participants. Any data collected to that date, including on cilostazol, will be retained and analysed according to the original study plan.

The proportion of total within-patient SAEs of any grade occurring until the end of the relevant wash out period or 30 days after taking the last tablet (whichever is greater) will be compared between a) sildenafil vs placebo and b) cilostazol vs placebo using McNemar's test. "Statistically significant excess" is defined as a statistically significant result at the 5% level i.e. a test with a p-value<0.05. Any statistically significant excess of SAEs in the treatment arm, or occurrence of unexpected treatment-related SAEs of sufficient severity (in the view of the DSMB), may result in early cessation of the study. The DSMB will review the total number of SAEs and AEs on a yearly basis, and the Chair of the DSMB will be informed of any SAEs that occur within 15 days of the event.

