5.4 Protocol pre-specified tertiary/exploratory analyses

The imaging analysis is specified in the protocol and this document. This will be completed and followed by the CI and relevant team members. Blood will be stored and then analysed at completion of the study, as the extent of testing will depend upon the demonstrated effect of medications in the study, whilst allowing for assessment of new biochemical and genetic markers reported during the study. Analysis of the markers of endothelial function and genetic targets of the trial medications (to be analysed in the two years after the last visit of the last participant) will also be detailed separately.

6. Safety data

Safety data will be routinely collected at each follow-up, including clinical history of side effects or adverse events, clinical examination and blood tests (FBC, U+Es, LFTs). The safety population will be used to summarise the adverse event data.

Adverse events (AEs) will be presented in tabular form a) per participant (see e.g. Table 6.1 below; all patients taking at least one tablet will be included) and b) per treatment administered in each period (e.g. see Table 6.2 below) including the wash-out (to a maximum of 30 days since the last tablet was taken). For each treatment within each patient, only the maximum severity of each type of AE will be displayed.

Table 6.1 Example of AE table

Adverse event (AE)		No. of participants	No. of AEs
e.g. Headache	No AE under any of the three treatments		
	No AE under sildenafil or cilostazol but AEs observed under placebo		
	No AE under sildenafil but AEs observed under placebo and cilostazol		

	AE observed under sildenafil but not under cilostazol or placebo		
	AE observed under sildenafil and cilostazol but not placebo		
	AE observed under sildenafil, cilostazol and placebo		

Table 6.2 Example of AE table

Period	Treatment	No. of participants taking treatment	No. of mild AEs	No. of moderate AEs	No. of severe AEs
First	Sildenafil				
	Cilostazol				
	Placebo				
Second	Sildenafil				
	Cilostazol				
	Placebo				
Third	Sildenafil				
	Cilostazol				
	Placebo				

SAEs are reportable for up to 30 days following the last administration of a trial drug whether after the end of a trial or between trial phases following a prolonged washout period and will be listed in full.

7. Statistical software

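### SAEs count for at least 30 days after the last tablet, but no contact is scheduled after Visit 3, so the window after treatment 3 is largely unasked and ascertainment differs between periods

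*Protocol*

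**What the plan says.** **The windows.** Protocol 10.4: "SAEs will be recorded and deemed reportable for up to 30 days following last administration of a trial drug". The same sentence extends this past the end of the trial and into prolonged washouts. For the McNemar comparisons of sildenafil and of cilostazol with placebo, SAP 2.4 counts SAEs "occurring until the end of the relevant wash out period or 30 days after taking the last tablet (whichever is greater"). A significant excess may lead to early cessation. For AEs, SAP section 6 tabulates events per treatment and period, "including the wash-out (to a maximum of 30 days since the last tablet was taken").

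**The contacts.** Protocol 10.1: "Safety data will be routinely collected at each follow-up". Protocol 8.6: "Participants will be reviewed at visits 2, 3 and 4 (3, 6-7 and 11-13 weeks respectively"). The schedule table calls these same three visits Visits 1 to 3 (days 28, 56 and 84) and has no later column. Protocol 8.10: "The end of active patient management is the date of the last visit of the last participant (LVLP"). Between visits, Protocol 10.1 offers a passive route: "Patients will also be provided a telephone number to contact in case of side effects".

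**The washout.** Protocol 8: "After visits 1 and 2, there will be a minimum of a 1 week washout period prior to starting the new medication". None is defined after the third treatment.

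**The concern.** The plan defines a period over which SAEs count but schedules no enquiry covering it after the third treatment. After treatments 1 and 2 the participant returns and is asked what happened in between. After treatment 3 nobody is due to ask.

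The plan has no rule for an unasked window, so it will be analysed as if no event occurred. The McNemar test pairs two treatments within one person. When one of the pair came third, its window was observed less completely than the other's. That test feeds a stopping consideration, and Tables 6.1 and 6.2 classify and count events by treatment and period. At stake are missed late SAEs after the final drug, period counts that do not mean the same thing, and lower power to detect an excess.

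**Working it through.** **Inputs.** Treatment 21 days and minimum washout 7 days (Protocol 6 and 8); SAE tail 30 days (Protocol 10.4, SAP 2.4); visit times (Protocol 8.6 and the schedule table); six sequences in groups of 12 or 13 (Protocol 6 and 8.4).

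**1. Timeline.** With minimum washouts, treatments end on day 21, day 21 + 7 + 21 = 49 and day 49 + 7 + 21 = 77, which are weeks 3, 7 and 11. This agrees with the weeks stated in Protocol 8.6 (3, 6-7 and 11-13). The schedule's 28-day spacing equals 21 + 7.

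**2. Tail days that precede a later scheduled visit.**

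| Treatment | Last tablet | Tail ends | Later visits | Days asked about |
|---|---|---|---|---|
| 1 | day 21 | day 51 | days 49 and 77 | 30 of 30 |
| 2 | day 49 | day 79 | day 77 | 28 of 30 |
| 3 | day 77 | day 107 | none | 0 of 30 |

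If dosing ends on day 77 but the visit is on the scheduled day 84, then 84 - 77 = 7 days are covered and 23 are not. The SAP 3.3 per-protocol population requires three doses in the 26 hours before assessment, so a conforming visit sits near the zero-coverage case. Longer washouts only improve coverage after treatment 2. The shortest course in Protocol 8 (7 days plus a minimum of 11) would give 7 + 18 = 25 of 30 after treatment 2.

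**3. Share of window days.** The SAE window for one treatment is 21 + 30 = 51 days.
- Unasked share of the third window: 30/51 = 59%, or 23/51 = 45% if 7 days are covered.
- Each drug is third for about one third of participants: 1/3 × 30/51 = 19.6% of that drug's total window days, or 1/3 × 23/51 = 15.0%.

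**4. Effect on drug against placebo.** Each drug is third in 2 of 6 sequences. With groups of 12 or 13 that is 24 to 26 of 75 participants, so the shortfall is nearly equal for all three drugs. SAP 2.2 instead describes simple randomisation. The difference between two drugs in the number given third would then have SD √(75 × (1/3 + 1/3)) = 7.1, or about ±14 participants (1.96 × 7.1).

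**5. Overlap.** With a 7-day washout, the 30-day tail runs 30 - 7 = 23 days past the start of the next treatment. That is all 21 days of it plus 2 more. Because SAP 2.4 takes the longer of the washout and 30 days, an SAE during treatment 2 can count for drug 1 and drug 2. Nothing follows treatment 3, so this too differs by period.

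**6. AE window (Table 6.2).** In periods 1 and 2 it is 21 + 7 = 28 to 21 + 30 = 51 days. In period 3 no washout is defined. The actively asked days are 21, or 28 if the visit falls 7 days after dosing, and the end of the window is not stated.

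**The case against.** The best defence is that the SAE window is a reporting obligation, deliberately wider than scheduled follow-up, and that safety is otherwise summarised descriptively (Protocol 11.1). Much of this stands, and it limits what can be claimed.

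- **Conflict with the follow-up duration.** A reader might infer a contradiction, because 77 + 30 = 107 days exceeds the synopsis limit of 15 weeks (105 days). The documents do not support this. Protocol 10.4 expressly reaches past the end of the trial, and a shorter permitted course, 3 × 18 + 2 × 7 = 68 days, gives 68 + 30 = 98.
- **Bias towards one drug.** A reader might infer that one drug's safety is flattered. Within any period all three drugs are ascertained alike, and each is third in a third of sequences. Apart from chance imbalance, the loss is of events and power.
- **A 30-day AE gap.** SAP section 6 makes 30 days a cap on the washout for AEs, not a promise. The 30-day gap concerns SAEs.
- **Nothing is captured after Visit 3.** Related AEs are followed to resolution or stability (Protocol 10.3), as are AEs that cause withdrawal (8.9), and participants can telephone. The gap is in new-onset events.
- **Stopping.** An SAE excess may, not must, stop the trial.

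The protocol figure is not shown and the SAP flow chart is stored separately, so a contact appearing only there cannot be excluded. None appears in the schedule table or text. The defence does not explain how the SAP 2.4 window is to be observed after treatment 3, and it does not remove the double counting.

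**Conclusion.** The point holds in this form. For a participant who completes the trial, 23 to 30 of the 30 days after treatment 3 have no scheduled enquiry, against 0 to 2 days after treatments 1 and 2. This makes period counts unequal and leaves the third drug under-ascertained within a participant's McNemar pair. Across participants the result is mainly lost events. The 15% to 20% is a share of days and should not be read as a share of events: the documents give no event rate, and much of the tail after a 1-week washout may be background time. The AE window in period 3 is shorter than in the other periods or undefined. Separately, the SAP 2.4 window can assign one SAE to two drugs when the washout is short.

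The day counts assume full three-week courses, at least a 7-day washout, and no contact recorded only in the missing figures.

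**What to change.** 1. **Schedule.** Add an AE/SAE telephone contact 30 days after the last tablet of treatment 3. Align the end of active management (Protocol 8.10) and the synopsis follow-up duration with it.
2. **Analysis.** In SAP 2.4 and Table 6.2, base the between-treatment comparison on first dose to that period's on-treatment visit. This interval is asked about in the same way in all three periods and assigns each event to one drug. List washout and post-treatment events separately, by the last drug taken.

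The first change alone makes the reporting window observable but leaves the overlap. The second makes the comparison symmetrical but does not find late events. Both are needed.

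**Cost.** Up to 75 short calls by existing staff, one schedule column, revised SAP wording, and completion about 30 days later. Washout events leave the formal comparison, so a delayed effect of the preceding drug would show only in the listing.

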10.5. Expectedness

Expectedness will be determined according to the Summary of Product Characteristics by the study principal investigator.

10.6. SUSAR Reporting

All SUSARs will be reported by the CI to the sponsor and the REC and other parties as applicable. For fatal and life-threatening SUSARs, this will be done no later than 7 calendar days after the Sponsor or delegate is first aware of the reaction. Any additional relevant information will be reported within 8 calendar days of the initial report. All other SUSARs will be reported within 15 calendar days. Events reported to the REC will use the HRA report of serious adverse event form (see HRA website).

Treatment codes will be un-blinded for specific participants.

Principal Investigators will be informed of all SUSARs for the relevant IMP for all studies with the same Sponsor, whether or not the event occurred in the current study.

10.7. Safety Monitoring Committee

A Data Safety and Monitoring Board will conduct a review of all SAEs for the study reported during the quarter and cumulatively. The aims of this committee include:

- To pick up any trends, such as increases in un/expected events, and take appropriate action
- To seek additional advice or information from investigators where required
- To evaluate the risk of the study continuing and take appropriate action where necessary

The Data and Safety Monitoring Board have reviewed the study protocol, will be informed of SAEs yearly, and will perform an interim safety assessment after 30 patients have been recruited (or 12 months have elapsed). If recruitment is excessively slow, the DSMB may recommend either that the study is stopped, or that the cilostazol phase of the study is removed and subsequent patients are only randomised to sildenafil vs placebo in random order. With removal of the third arm of the study, the overall population size would also be reduced to 50 patients.

11. STATISTICS

11.1. Description of Statistical Methods

A statistical analysis plan will be signed off prior to analysis.

Primary outcome :

Change in Gosling's Pulsatility Index from baseline to follow up, utilising the visually-assessed, better quality TCD recording (defined by blinded assessor) will be compared between sildenafil and placebo phases by paired T-test, comparing change in MCA-PI from baseline to after 3 weeks of treatment.

Secondary outcome:

The non-inferiority analysis will be based on the 95% CI for the mean change difference between sildenafil and cilostazol. If the upper 97.5% confidence limit is less than 0.08 units (2/3 of the clinically estimated overall cilostazol effect), non-inferiority will be declared.

Differences in reactivity to CO₂ from baseline in each of three states (sildenafil, cilostazol, placebo) will be compared by mixed-effect general linear models, with post-hoc pairwise comparison.

Tertiary outcomes

Equivalent statistical techniques will be used to determine responses to each of the further physiological measures for sildenafil versus placebo as the primary comparison (paired t-test for continuous outcomes), and mixed-effect linear models across the three groups. MRI imaging outcomes will be compared by analysis tools within the FSL software library, utilising linear models for interaction between drug allocation and BOLD-response to carbon dioxide. Secondly, the relevance of derived physiological indices including home blood pressure, arterial stiffness, cerebral autoregulation, peripheral vascular reactivity and beat-to-beat blood pressure variability will be determined both as predictors of cerebral pulsatility and autoregulation in linear models, and for the interaction between drug class and these indices on cerebral pulsatility and reactivity.

Individuals missing either sildenafil or placebo interventions will be excluded from the analysis corresponding to the primary objective but included in the safety analysis. Participants without cilostazol exposure will be included in the sildenafil-placebo comparison, but not in the - secondary and tertiary analyses.

Safety data will be presented for all patients who are randomised and receive at least one dose of one treatment. Safety data will be summarised descriptively.

Genetic / biochemical predictors of response to treatment will be assessed by mixed linear models for continuous outcomes, and paired t-test for binary measures.

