5. OBJECTIVES AND OUTCOME MEASURES

[figure not shown]
Objectives	Outcome Measures	Timepoint(s)
Primary Objective Assess whether 3 weeks of treatment with sildenafil (a PDE5 inhibitor) reduces cerebral arterial pulsatility on transcranial ultrasound, compared to placebo in patients with chronic vascular injury to the brain (small vessel disease)	Middle cerebral arterial pulsatility index ((Gosling's PI = peak systolic velocity – end diastolic velocity)/(mean flow velocity)) on transcranial ultrasound	Baseline, after 3 weeks of treatment with placebo versus 3 weeks of sildenafil
Secondary Objectives 1) Assess whether 3 weeks of treatment with sildenafil (a PDE5 inhibitor) alters cerebral arterial reactivity to carbon dioxide on transcranial ultrasound, compared to placebo 2) Assess whether 3 weeks of treatment with sildenafil (a PDE5 inhibitor) has non-inferior effects on cerebral arterial pulsatility and reactivity to carbon dioxide on transcranial ultrasound, compared to cilostazol (a PDE 3 inhibitor)	Percentage increase in MCA velocity on 6% CO ₂ vs medical air As above	As above
Tertiary Objectives 1) Assess whether 3 weeks of treatment with sildenafil (a PDE5 inhibitor) or cilostazol increases cerebral arterial reactivity to carbon dioxide on MRI, compared to placebo 2) Determine biochemical / genetic predictors of response to treatment	Reactivity of BOLD signal on MRI to CO ₂ challenge Markers of endothelial function (e.g. ICAM, VEGF, vWF) and genetic targets of the medications in the trial	After 3 weeks of treatment with sildenafil or cilostazol versus placebo Analysed in the 2 years after the last visit of the last participant.

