1.3 Trial objectives

Primary objective

To assess whether 3 weeks of treatment with sildenafil (a PDE5 inhibitor) reduces cerebral arterial pulsatility on transcranial ultrasound, compared to placebo in patients with chronic vascular injury to the brain (small vessel disease).

Secondary objectives

1. To assess whether 3 weeks of treatment with sildenafil alters cerebral arterial reactivity to carbon dioxide on transcranial ultrasound, compared to placebo (The null hypothesis is that there is no difference in the mean change between the sildenafil and placebo groups)
2. To assess whether 3 weeks of treatment with sildenafil has non-inferior effects on cerebral arterial pulsatility and reactivity to carbon dioxide on transcranial ultrasound, compared to cilostazol (The null hypothesis is that sildenafil is unacceptably inferior to cilostazol i.e. the change in mean flow velocity upon CO₂ challenge with sildenafil differs from that with cilostazol by more than the non-inferiority margin Δ).

3. To assess whether 3 weeks of treatment with sildenafil or cilostazol increases cerebral arterial reactivity to carbon dioxide on MRI, compared to placebo, in normal appearing white matter and within white matter hyperintensities.

Tertiary objectives (exploratory and mechanistic)

1. To assess whether 3 weeks of treatment with sildenafil or cilostazol increases cerebral arterial reactivity to carbon dioxide on MRI, compared to placebo, for all defined cerebral tissue type (all white matter and grey matter) and on a voxel-wise basis.
2. To assess whether there is an increased incidence of adverse events or serious adverse events with sildenafil or cilostazol compared to placebo.
3. To assess whether 3 weeks of treatment with sildenafil or cilostazol affects the following physiological parameters, compared to placebo:
 - a) Systolic and diastolic blood pressure on 1 week of home blood pressure monitoring
 - b) Arterial stiffness (carotid-femoral pulse wave velocity)
 - c) Aortic pulse pressure
 - d) Beat-to-beat and day-to-day variability in systolic blood pressure
 - e) Flow mediated slowing
 - f) Resting state cerebral autoregulation (transfer function analysis derived gain, phase and coherence between beat-to-beat blood pressure and cerebral blood flow velocity during a minimum of 5 minutes of monitoring).

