5.2 Secondary outcomes

The percentage change in mean blood flow velocity per mmHg during inhalation of air, 4% and 6% carbon dioxide versus medical air estimated from the beta-coefficient from a phase-shifted linear regression will be compared between sildenafil and placebo treatment by paired t-test and a 95% confidence interval if normality distribution assumptions hold, or the non-parametric Wilcoxon signed rank test. The analysis will be re-run using the PP population as a sensitivity analysis, and using the percentage change from baseline.

A non-inferiority analysis will be based on the 95% CI for the mean change difference between sildenafil and cilostazol. If the upper 97.5% confidence limit is less than 0.08 units (=inferiority margin, 2/3 of the clinically estimated overall cilostazol effect), non-inferiority will be declared. The data will be transformed if normality assumptions do not hold. The PP population will be used for this analysis, with the ITT population being used in a sensitivity analysis.

Differences in reactivity to CO₂ from baseline in each of three states (sildenafil, cilostazol, placebo) will be compared by mixed-effect general linear models, with post-hoc pairwise comparison, using the ITT population with the PP population being used in a sensitivity analysis. This will apply to both TCD measures of CO₂ reactivity and by ROI on MRI. On MRI, these analyses will also be performed on a voxel-wise basis by use of the FLAME tool (FSL).

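### Read literally, Protocol 11.1 drops participants without cilostazol exposure from sildenafil-placebo analyses that need no cilostazol data. The loss is small unless the cilostazol phase is removed, but the sentence should be narrowed.

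*Protocol*

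**What the plan says.** Protocol 11.1 has two inclusion rules. The first removes anyone missing sildenafil or placebo from the analysis of the primary objective. The second concerns cilostazol: "Participants without cilostazol exposure will be included in the sildenafil-placebo comparison, but not in the - secondary and tertiary analyses". It names no exceptions.

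Several secondary and tertiary analyses compare only sildenafil with placebo:

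- Secondary objective 1 in Protocol section 5 asks whether sildenafil "alters cerebral arterial reactivity to carbon dioxide on transcranial ultrasound, compared to placebo". SAP 1.3 repeats it, and SAP 5.2 says the measure "will be compared between sildenafil and placebo treatment by paired t-test and a 95% confidence interval if normality distribution assumptions hold".
- For the further physiological measures, Protocol 11.1 itself names "sildenafil versus placebo as the primary comparison (paired t-test for continuous outcomes").
- The three-treatment mixed models for CO2 reactivity (Protocol 11.1, SAP 5.2) are followed by pairwise comparisons, one of which is sildenafil against placebo.

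On populations, Protocol 11.6 uses all possible data by intention to treat. SAP 3.3 defines the ITT set as everyone randomised, whatever treatment they received. SAP 5.2 uses that set for the mixed models, with the per-protocol set as a sensitivity analysis. The SAP does not mention the cilostazol exclusion.

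Protocol 10.7 adds a contingency. If recruitment is too slow, the safety board may recommend that "the cilostazol phase of the study is removed and subsequent patients are only randomised to sildenafil vs placebo in random order", with the total reduced to 50.

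**The concern.** A participant who has taken and been assessed on both sildenafil and placebo supplies everything a sildenafil-placebo contrast needs. Barring that person because a third treatment was never started costs precision and gains nothing. The primary and secondary sildenafil-placebo results would then rest on different sets of people.

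The exclusion would also depend on sequence. When a participant simply withdraws, a complete sildenafil-placebo pair without cilostazol can arise only in sequences 1 and 5, where cilostazol comes last.

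Two analysts could reach different analysis sets and both claim to follow the plan, one applying the protocol sentence and the other the SAP's populations. For the first-listed secondary objective, that choice should not be open once allocations are known.

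If cilostazol were removed under Protocol 10.7, every later participant would lack cilostazol exposure and fall under the bar.

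**Working it through.** **The plan's own figures.** The sample-size figures in Protocol 11.3 and SAP 2.3 reproduce and are not in dispute.

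- Primary: a difference of 0.12, SD of differences 0.2, two-sided 5% and 90% power give 32 by paired t-test (power 0.908). 32/0.85 = 37.6, so 38.
- Non-inferiority: margin 0.08 and within-subject variance 0.02, so the SD of differences is √(2 × 0.02) = 0.2. The normal approximation gives 65.67, so 66. 66/0.88 = 75.

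The documents give no figure for the share excluded by the cilostazol rule. It is derived here.

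**Which analyses need cilostazol data?**

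| Analysis | Cilostazol value needed? | Barred by the literal rule? |
|---|---|---|
| Primary: MCA-PI, sildenafil vs placebo | No | No |
| Secondary objective 1: CO2 reactivity on TCD, sildenafil vs placebo | No | Yes |
| Non-inferiority, sildenafil vs cilostazol | Yes | Yes |
| Three-treatment mixed models | No; two observed states can contribute | Yes |
| Tertiary paired t-tests, sildenafil vs placebo | No | Yes |

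Only in the non-inferiority row does the exclusion follow from the analysis itself.

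**Measure of cost.** The half-width of the 95% interval for a paired mean, in SD units, is h(n) = t(0.975, n−1)/√n. The ratio of half-widths shows how much wider the interval becomes.

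**Case A: all three treatments kept.**

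- Ceiling: suppose all the planned 12% dropout (0.12 × 75 = 9) complete sildenafil and placebo but never start cilostazol. Then 66 pairs remain instead of 75. h(66)/h(75) = 0.2458/0.2301 = 1.07.
- More likely: spread the 9 evenly over six sequences (an assumption). Sequences 1 and 5 then have 9 × 2/6 = 3, and only those who stop between periods 2 and 3 count. Even if all 3 did, 66 pairs remain instead of 69: h(66)/h(69) = 0.2458/0.2402 = 1.02.

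**Case B: cilostazol removed under Protocol 10.7, total 50, no other dropout assumed.** With k patients recruited under the three-treatment design, the excluded share is (50 − k)/50.

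| k at removal | Excluded | h(k) | h(k)/h(50), h(50) = 0.2842 |
|---|---|---|---|
| 35 | 15/50 = 30% | 0.3435 | 1.21 |
| 30 | 20/50 = 40% | 0.3734 | 1.31 |
| 17 | 33/50 = 66% | 0.5142 | 1.81 |

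The row for 30 is the patient count that triggers the review. The row for 17 uses the 12-month trigger and the advisory pace in Protocol 11.4 (35 in 2 years, so about 17 in one year, assuming a constant rate).

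**Power.** The documents give no design effect for CO2 reactivity, so power can only be illustrated. If the pulsatility design effect is borrowed (0.12/0.2 = 0.6 SD), power is 0.99 with 50 pairs and 0.89 with 30. For an assumed effect of 0.4 SD it is 0.79 and 0.56.

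**The case against.** The strongest reply is that the SAP governs the analysis and already does the sensible thing. SAP 1.1 says the reported results should follow its strategy. SAP 5.2 sets no cilostazol condition on the sildenafil-placebo test, and the per-protocol set in SAP 3.3 requires completion only of the treatments relevant to each analysis. SAP 5.1 also departs from the protocol sentence just before this one, because it accepts baseline against sildenafil when placebo is missing. So the inclusion rules of Protocol 11.1 do not simply carry over.

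Much of this stands: an analyst working only from the SAP would probably not apply the exclusion. But the change on missing placebo is explicit, and on cilostazol the SAP is silent while stating that it is based on the latest protocol. SAP 3.3 ties the ITT set to the primary aim and to safety, and SAP 5.2 names no main population for the secondary paired t-test, only a per-protocol sensitivity analysis. The conflict is therefore left open.

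The protocol sentence also has a stray hyphen where a word may have been lost, and its first half can be read as covering sildenafil-placebo comparisons in general. A narrower rule may have been meant. That is a reason to clarify it, since the text as it stands does not say so.

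Finally, the secondary sildenafil-placebo paired t-test appears only in the SAP. Within the protocol alone, the conflict is with the tertiary paired t-tests, the two-state contributions to the mixed models (including their sildenafil-placebo contrast), and section 11.6. This narrows the internal contradiction but does not remove it.

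**Conclusion.** The concern holds as a should-fix. The literal rule excludes valid sildenafil-placebo pairs without statistical reason and is not reconciled with Protocol 11.6 or the SAP. With three treatments, the cost is at most about 9 of 75 participants and probably a few. With removal of cilostazol at exactly 30 patients it is 20 of 50, assuming no other dropout.

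A reader might infer more than the documents support:

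- *That the plan discards 40% or more of the pairs.* This needs the safety board to use the Protocol 10.7 option. SAP 2.4 keeps the possible reduction to 50 but does not mention removing cilostazol, and SAP section 2 still describes three arms. Nor is 40% a bound in either direction.
- *That about 25 of 75 participants, those in sequences 1 and 5, would be lost.* They are the ones in whom ordinary withdrawal could trigger the rule. Only those who complete both earlier periods and never start cilostazol are affected.
- *That the primary result is at risk.* The sentence expressly keeps these participants in the sildenafil-placebo comparison.
- *That MRI participants scanned only on sildenafil and placebo are barred.* The rule concerns exposure, and those participants take cilostazol even though they are not scanned on it.

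**What to change.** Replace the sentence in Protocol 11.1, and state the same in SAP 3.3 and 5.2:

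> Participants without cilostazol data are excluded only from pairwise comparisons that involve cilostazol; they are included in every sildenafil-placebo secondary and tertiary analysis for which they have data, and contribute their available states to the three-treatment mixed models.

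The cost is one sentence in each document, agreed before unblinding. No new data, visits or participants are needed, and the sample size does not change. With this wording, up to 50 of 50 pairs (before dropout) would stay in the sildenafil-placebo secondary and tertiary analyses even if cilostazol were removed.
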